4.2.1 Participant input into design

Not applicable.

4.3 JUSTIFICATION FOR DOSE

The dose of 10 mg (11 mg per US/Canada label) was chosen based on a PK/PD model characterizing the relationship between drug exposure and pharmacodynamic effect. The adequacy of the dosing regimen was validated in aTTP patients in the Phase 2 ALX-0681-2.1/10 (TITAN) study and the Phase 3 ALX0681-C301 (HERCULES) study. The initial 10 mg IV bolus aimed to achieve immediate neutralization of vWF, subsequently maintained by the daily 10 mg SC dosing regimen, for a fast normalization of platelet counts.

4.4 END OF STUDY DEFINITION

A participant is considered to have completed the study if he/she has completed all periods of the study including the last scheduled procedure shown in the Schedule of Activities ([Section 1.3](#)).

The end of the study is defined as the date of the last visit of the last participant in the study or last scheduled procedure shown in the Schedule of Activities for the last participant in the trial.

5 STUDY POPULATION

Prospective approval of protocol deviations to recruitment and enrollment criteria, also known as protocol waivers or exemptions, is not permitted.

5.1 INCLUSION CRITERIA

Participants are eligible to be enrolled in the study only if all of the following criteria apply:

Age

I 01. Participant must be 18 to 80 years of age, inclusive, at the time of signing the informed consent.

Type of participant and disease characteristics

I 02. Participants with a clinical diagnosis of iTTP (initial or recurrent), which includes thrombocytopenia, microangiopathic hemolytic anemia (eg, presence of schistocytes in peripheral blood smear) and relatively preserved renal function. The iTTP diagnosis should be confirmed by ADAMTS13 testing within 48 hours (2 days).

I 03. Participants with a clinical diagnosis of iTTP and a French TMA score of 1 or 2.

Note: French Score is a clinical scoring system that predicts severe ADAMTS13 deficiency in those with features of thrombotic microangiopathy (TMA). A French Score of 2 (platelet count $\leq 30 \times 10^9/L$ and serum creatinine $\leq 2.27 \text{ mg/dL}$) is considered highly suggestive of iTTP. Those with a French Score of 1 (either platelet count $\leq 30 \times 10^9/L$ or serum creatinine $\leq 2.27 \text{ mg/dL}$) will be considered having probable iTTP (29).

Weight

Not applicable.

Sex, contraceptive/barrier method and pregnancy testing requirements/breastfeeding

I 04. All

Contraceptive use by men and women should be consistent with local regulations regarding the methods of contraception for those participating in clinical studies.

a) Male participants

Male participants with female partners of childbearing potential must agree to follow the contraceptive guidance in Appendix 4 ([Section 10.4](#)) during the overall treatment period and for at least 2 months after last study drug administration.

b) Female participants

- A female participant is eligible to participate if she is not pregnant or breastfeeding, and one of the following conditions applies:
 - Is a woman of nonchildbearing potential (WONCBP) as defined in Appendix 4 Contraceptive and barrier guidance ([Section 10.4](#)),

OR

- Is a woman of childbearing potential (WOCBP) and agrees to use an acceptable contraceptive method (as described in [Section 10.4](#)) during the study intervention period and for at least 2 months after the last administration of study intervention. The Investigator should evaluate the potential for contraceptive method failure (eg, noncompliance, recently initiated) in relationship to the first administration of study intervention.
- A WOCBP must have a negative highly sensitive pregnancy test (urine or serum as required by local regulations) during Screening before the first administration of study intervention, see [Section 8.2.5](#) Pregnancy testing. If a urine test cannot be confirmed as negative (eg, an ambiguous result), a serum pregnancy test is required. In such cases, the participant must be excluded from participation if the serum pregnancy result is positive.

Informed Consent

I 01. Capable of giving signed informed consent as described in Appendix 1 of the protocol which includes compliance with the requirements and restrictions listed in the informed consent form (ICF) and in this protocol.

5.2 EXCLUSION CRITERIA

Participants are excluded from the study if any of the following criteria apply:

Medical conditions

E 01. Platelet count $\geq 100 \times 10^9/L$.

E 02. Serum creatinine level $> 2.26 \text{ mg/dL}$ ($200 \mu\text{mol/L}$) in case platelet count is $> 30 \times 10^9/L$ (to exclude possible cases of atypical HUS).

E 03. Known other causes of thrombocytopenia including but not limited to:

- Clinical evidence of enteric infection with *E. coli* 0157 or related organism.
- Atypical HUS.
- Hematopoietic stem cell, bone marrow or solid organ transplantation-associated thrombotic microangiopathy.
- Known or suspected sepsis.
- Diagnosis of disseminated intravascular coagulation.

- E 04. Congenital TTP (known at the time of study entry).
- E 05. Clinically significant active bleeding or known co-morbidities associated with high risk of bleeding (excluding thrombocytopenia).
- E 06. Inherited or acquired coagulation disorders.
- E 07. Malignant arterial hypertension.
- E 08. Participants requiring or expected to require invasive procedures immediately (eg, stroke requiring thrombolytic therapy, those who need mechanical ventilation, etc.).
- E 09. Those presenting with severe neurological (ie, coma, seizures, GCS \leq 8, stroke) or severe cardiac disease (per Investigator's discretion or cTnI $> 5 \times$ ULN, or cTnT $> 5 \times$ ULN, high sensitivity cTnT $> 5 \times$ ULN, or high sensitivity cTnI $> 5 \times$ ULN). The preferred assessment is cTnI, but cTnT, high sensitivity cTnT, or high sensitivity cTnI may be used if cTnI is unavailable.
- E 10. Clinical condition other than that associated with TTP, with life expectancy <6 months, such as end-stage malignancy.

Prior/concomitant therapy

- E 11. Known chronic treatment with anticoagulants and anti-platelet drugs that cannot be stopped (interrupted) safely, including but not limited to:
 - vitamin K antagonists.
 - direct-acting oral anticoagulants.
 - heparin or low molecular weight heparin (LMWH).
 - non-steroidal anti-inflammatory molecules other than acetyl salicylic acid.

Prior/concurrent clinical study experience

- E 12. Participants who were previously enrolled in this clinical study (study EFC16521).
- E 13. Participants who received an investigational drug, or device, other than caplacizumab, within 30 days of anticipated IMP administration or 5 half-lives of the previous investigational drug, whichever is longer. However, participants who have received any dose(s) of caplacizumab for the presenting episode of iTTP more than 4 hours before enrollment in Study EFC16521 are also excluded.

Diagnostic assessments

- E 14. Positive result on the Screening SARS-CoV-2 reverse transcription polymerase chain reaction (RT-PCR) test or on SARS-CoV-2 antigen test.

Other exclusions

- E 15. Sensitivity to any of the study interventions, or components thereof, or drug or other allergy that, in the opinion of the Investigator, contraindicates participation in the study.
- E 16. Individuals accommodated in an institution because of regulatory or legal order; prisoners or participants who are legally institutionalized.
- E 17. Participant not suitable for participation, whatever the reason, as judged by the Investigator, including medical or clinical conditions, or participants potentially at risk of noncompliance to study procedures.
- E 18. Participants are employees of the clinical study site or other individuals directly involved in the conduct of the study, or immediate family members of such individuals (in conjunction with section 1.61 of the ICH-GCP Ordinance E6).

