There is limited availability of data on efficacy of caplacizumab without TPE as first-line therapy. There are published case reports for 11 acute episodes in 10 patients (2, 25, 26, 27, 28), treated with caplacizumab and immunosuppression without requiring TPE. All had platelet count recovery within 5 days. In the published case series by Volker et al, the platelet counts normalized ($>150 \times 10^9/L$) after median 84 hours (3.5 days) with a range of 48 hours to 96 hours (2- 4 days) (2). In the Phase 3 HERCULES study, the median time to normalization of the platelet count was shorter with caplacizumab than with placebo (2.69 days [95% CI, 1.89 to 2.83] vs. 2.88 days [95% CI, 2.68 to 3.56], $P = 0.01$). However, it is important to note that all HERCULES study patients had a TPE prior to study entry, and this may have shortened the time to platelet response. In the Phase 2 TITAN study, the median time to confirmed platelet response was 2.97 days (95% CI: 2.74, 3.65) in the caplacizumab group and 4.79 days (95% CI: 3.51, 5.94) in the placebo group. Majority of the patients in the TITAN study did not receive a prior TPE.

In summary, treatment with caplacizumab and immunosuppression without first-line TPE may reduce the morbidity and mortality associated with TPE-related complications. It will improve

[figure not shown]
patients' quality of life while reducing the overall iTTP related health care resource utilization and costs (ie, the number of days in intensive care unit (ICU), length of hospitalization and number of days and volume of plasma needed if requires TPE). Although, there is limited availability of data on efficacy of caplacizumab/Cablivi® without TPE as first-line therapy, there are published case reports for 11 acute episodes in 10 patients, treated with caplacizumab and IST without TPE. All patients showed platelet count recovery within 5 days and no new safety findings were reported.

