Study participants will not receive TPE as first-line therapy. However, participants may receive TPE if it is determined that there is lack of adequate response to treatment after first 24 hours or if there is any clinical deterioration at any time during the study, including during the first 24 hours (please see below for additional details). It is expected that the participant is hospitalized when the treatment is started, and the duration of initial hospitalization may vary based on clinical condition of the individual participant.

Caplacizumab treatment will be continued until sustained ADAMTS13 activity level of $\geq 50\%$ at 2 consecutive visits after platelet count normalization (defined as $\geq 150 \times 10^9/L \times 2$ consecutive values) or 12 weeks, whichever occurs first. Thus, the maximum treatment duration of caplacizumab will be 12 weeks for the presenting episode.

The post-treatment follow-up period will be 12 weeks. The anticipated study duration per participant without a recurrence while on therapy is maximum of approximately 24 weeks (ie, approximately 1 day for screening + maximum 12 weeks of treatment for the presenting episode + 12 weeks of follow-up).

Initial treatment regimen during hospitalization:

1. anti-vWF therapy: Caplacizumab

Recommended dose: Caplacizumab 10 mg (11 mg in US and Canada; see [Section 2](#)) intravenous (IV) for a single dose followed by caplacizumab 10 mg (11 mg in US and Canada) subcutaneous (SC) 4-6 hours after the IV dose (Day 1) (exceptions to this are detailed in [Section 1.3.4](#)). This will be followed by caplacizumab 10 mg (11 mg in US and Canada) SC daily starting on Day 2 for a maximum treatment duration of 12 weeks.

Note: The baseline ADAMTS13 activity level results from the local laboratory, available within 48 hours will be used to confirm the diagnosis of iTTP. It is expected that there will be minimal discrepancy between local and central laboratory ADAMTS13 activity levels. The central laboratory test results will be available only after 3-4 days.

- If the baseline central laboratory ADAMTS13 activity is <10% of normal → continue caplacizumab and IST.
- If the baseline central laboratory ADAMTS13 activity is between 10% - 20% of normal → use clinical judgment in deciding to continue or stop caplacizumab treatment after evaluation of the totality of signs and symptoms plus other laboratory data.

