9.1 POPULATIONS FOR ANALYSES

The following populations for analyses are defined:

Table 6 - Populations for analyses

Population	Description
Intent-to-treat (ITT)	All enrolled participants, regardless of whether the investigational medicinal product (IMP) was received or not.
Modified ITT (mITT)	All participants from ITT population who received at least 1 dose of IMP and with an evaluable primary endpoint. The primary endpoint is evaluable when the following condition is met: The participant has an ADAMTS13 activity <10% at baseline.
Safety	All enrolled participants who take at least 1 dose of IMP.
Pharmacokinetic (PK)	All enrolled and treated participants (safety population) with at least one post-baseline PK sample with adequate documentation of dosing and sampling dates and times.

Enrolled participants for whom it is unclear whether they took the study intervention will be considered as exposed and will be included in the safety population.

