9.2.1 General considerations

In general, continuous data will be summarized using the number of observations available, mean, SD, median, [Q1, Q3], minimum, and maximum, where appropriate. Categorical and ordinal data will be summarized using the count and percentage of participants.

No pre-specified success criterion and formal statistical hypothesis testing is planned.
No statistical adjustment on interim analyses.

The baseline value is defined as the last available value before the first dose of open-label IMP. For participants enrolled but not treated, the baseline value is defined as the last available value before enrollment.

The observation period will be divided into 4 segments:

- The **pre-treatment period** is defined as the period up to first IMP administration.
- The **treatment-emergent (TE) period** is defined as the period from the first IMP administration to the last IMP administration + 28 days. The treatment-emergent period includes the following 2 periods:
 - The **on-treatment period** is defined as the period from the first IMP administration to the last administration of the IMP,
 - The **residual treatment period** is defined as the period from the end of the on-treatment period to the end of the treatment-emergent period.
- The **post treatment-emergent (TE) period** is defined as the period from the end of the treatment emergent period.

The **overall study period** for analysis is defined as the time from first IMP administration until the end of the study.

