9.2.2 Primary endpoint(s) analyses

The primary endpoint will be analyzed in mITT population.

The primary endpoint is the proportion of participants achieving remission without requiring TPE during the overall study period. Remission is defined as sustained Clinical Response with either (a) no TPE and no anti-VWF therapy for ≥ 30 days (Clinical Remission) or (b) with attainment of ADAMTS13 activity level $\geq 50\%$ (Complete ADAMTS13 Remission), whichever occurs first. Remission is assessed starting from the clinical response (for participants not requiring TPE) or the end of TPE (for participants requiring TPE), until the end of study.

Clinical response is defined as sustained platelet count $\geq 150 \times 10^9/L$ and LDH $< 1.5 \times$ ULN and no clinical evidence of new or progressive ischemic organ injury for at least 2 consecutive visits.

Clinical remission is defined as sustained Clinical Response with no TPE and no anti-vWF therapy for ≥ 30 days.

Complete ADAMTS13 Remission is defined as sustained Clinical Response with attainment of ADAMTS13 activity level $\geq 50\%$ for at least 2 consecutive visits during the overall study period.

Responders are participants who achieve remission without requiring TPE during the overall study period. Each participant will be classified as a responder or non-responder per the response criteria, and the proportion of responders will be calculated together with a 95% Wilson CI.

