3 STATISTICAL ANALYSES

3.1 GENERAL CONSIDERATIONS

In general, continuous data will be summarized using the number of observations available, mean, standard deviation (SD), median, interquartile range (Q1, Q3), minimum, and maximum.

Categorical and ordinal data will be summarized using the count and percentage of participants.

No pre-specified success criterion or formal statistical hypothesis testing is planned. No statistical adjustment on interim analyses is planned.

When the notion of IMP is mentioned in the SAP, this refers to the study IMP.

The baseline value is defined as the last available value before the first dose of IMP, including participants who have received a dose of marketed caplacizumab for the presenting episode of iTP within 4 hours prior to enrollment. For participants enrolled but not treated with IMP, the baseline value is defined as the last available value before enrollment.

Efficacy endpoints derived from laboratory data (platelet count, lactate dehydrogenase [LDH], cardiac troponin I [cTnI], creatinine, ADAMTS13 activity) will be analyzed using central measurements, unless they are missing for a visit but the local value available, in which case the local value will be used under certain conditions (see [Section 5.4](#)). A central measurement will be considered missing if the recorded status is “NOT DONE” and there is a reason for this status or if status is “NOT PERFORMED”.

The observation period will be divided into 4 segments:

- The **pre-treatment period** is defined as the period up to the first caplacizumab administration (whatever marketed or study IMP).
- The **treatment-emergent (TE) period** is defined as the period from the first caplacizumab administration (whatever marketed or study IMP) up to the last caplacizumab administration **+ 28 days**. The TE period includes the following 2 periods:
 - The **on-treatment period** is defined as the period from the caplacizumab administration (whatever marketed or study IMP) to the last administration of caplacizumab.
 - The **residual treatment period** is defined as the period from the end of the on-treatment period to the end of the TE period.
- The **post TE period** is defined as the period from the end of the TE period.

The **overall study period** is defined as the time from the first caplacizumab administration (whatever marketed or study IMP) until the end of the study.

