- The values resulting from these derivations will be the values used for the graphical representation of platelet, LDH and ADAMTS13 activity from Day 4.

Consecutive laboratory assessments are considered as 'consecutive visits' for efficacy endpoints.

A participant could potentially have missing laboratory assessment data, however, remission could still be confirmed at a subsequent laboratory value. In the case there is inadequate information to determine the remission status of a participant by the end of the study, the participant will be treated as not having achieved remission.

Clinical evidence of new or progressive ischemic organ injury

Clinical evidence of new or progressive ischemic organ injury is defined as any presence of following clinically significant iTTP event:

- Neurological event
- Elevated cardiac troponins
- Acute myocardial infarction
- Conduction abnormality
- Repolarization abnormality
- Heart failure
- Clinically significant renal event

which will be identified from the checkboxes in the "Clinically Significant TTP Event" eCRF form.

Exacerbation of TTP, Relapse of TTP and Other event will not be considered as clinical evidence of new or progressive ischemic organ injury.

Sustained Clinical Response

Sustained Clinical response is defined by the concomitance of the 3 following criteria for at least 2 consecutive visits (starting from D2):

- platelet count $\geq 150 \times 10^9/L$
- LDH $< 1.5 \times ULN$
- no clinical evidence of new or progressive ischemic organ injury

Remission

Remission is defined as (1) a sustained Clinical response (see above) associated with (2) Clinical remission or (3) Complete ADAMTS13 Remission, whichever occurs first, and defined as:

- Clinical remission: No TPE (*Plasma Exchange* form) and no anti-VWF therapy (Caplacizumab treatment) for ≥ 30 days (from the date that Clinical Response is achieved).
- Complete ADAMTS13 Remission: The attainment of ADAMTS13 activity level $\geq 50\%$ for at least 2 consecutive visits (starting from D2).

Time to event

For each of below time to event, in case of no observation of the event or death, the censoring date will be defined as the last non-missing value of the analyzed parameter (platelet count, LDH....) if any, else as the start date of treatment (defined as first caplacizumab administration [whatever marketed or study IMP]).

- Time to platelet count response will be calculated as follow:

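### Plasma exchange given for the presenting episode before any caplacizumab is neither addressed at entry nor counted in the primary endpoint, so an already exchanged participant can be scored as a TPE-free remission

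*Protocol*

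**What the plan says.** **Eligibility.** Protocol 5.1 and 5.2 do not mention TPE, plasma exchange or plasma infusion. The one limit on earlier treatment of the presenting episode is in E 13, which excludes "participants who have received any dose(s) of caplacizumab for the presenting episode of iTTP more than 4 hours before enrollment".

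**Responder rule.** Protocol 9.2.2: "Responders are participants who achieve remission without requiring TPE during the overall study period". SAP 3.2.1 has the same rule.

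**Start of the counting period.** In Protocol 9.2.1 the overall study period "for analysis is defined as the time from first IMP administration until the end of the study". In SAP 3.1 it "is defined as the time from the first caplacizumab administration (whatever marketed or study IMP) until the end of the study".

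**Remission routes.** SAP 5.4 runs the 30-day period free of TPE and anti-vWF therapy "from the date that Clinical Response is achieved". The ADAMTS13 route has no TPE condition of its own.

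**Primary population.** The mITT filter in Protocol 9.1 is: "The participant has an ADAMTS13 activity <10% at baseline". Baseline is the last value before the first study dose.

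**Design.** Protocol 4.1: "Study participants will not receive TPE as first-line therapy".

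**Why earlier TPE matters.** Protocol 2.3.2 notes that "all HERCULES study patients had a TPE prior to study entry, and this may have shortened the time to platelet response". Protocol 2.2 says that TPE restores ADAMTS13 and removes the antibodies against it.

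**The concern.** The eligibility list and the responder rule leave the same gap. Nothing at entry stops a participant who has just been exchanged, and nothing in the endpoint looks back to find the exchange. Followed as written, the plan can report such a participant as evidence that TPE was not needed.

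The gap bears on the trial's central question. Clinical Response includes platelet recovery, and the Protocol itself accepts that a prior exchange may speed it. Standard care as described in Protocol 2.2 includes TPE, and screening may start on Day -2, so an exchange before enrolment is conceivable. The current text already provides for caplacizumab given before enrolment, but has no matching provision for TPE or plasma. Plasma infusion without exchange does not enter the endpoint at any time.

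**Working it through.** **1. Which exchanges count.**

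| Timing of TPE for the presenting episode | Protocol 9.2.1 | SAP 3.1 |
|---|---|---|
| Before any caplacizumab | not counted | not counted |
| After a marketed dose, before the first study dose | not counted | counted |
| After the first study dose | counted | counted |

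The middle row is where the two documents disagree. That window is short: under Protocol 1.3.4 the first study dose is then due 4 to 6 hours after the marketed dose. The first row is uncounted under both.

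**2. Whether another rule catches the first row.**
- E 01 removes only those with platelets already at 100 × 10⁹/L or more.
- E 17 lets the investigator exclude an unsuitable patient but does not require it.
- The mITT filter removes a participant whose baseline ADAMTS13 has been lifted to 10% or more; one still below 10% stays.
- The FAS sensitivity analysis (SAP 3.2.3) drops the ADAMTS13 filter and reclassifies nobody.
- SAP 5.3 summarises prior medications and describes TPE by time since first caplacizumab, but neither feeds responder status.

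Each safeguard is partial or optional.

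**3. The plan's own figure.** Inputs from Protocol 9.4: n = 55; assumed rate 70%, from 85% remission and 18% requiring TPE (0.85 × 0.82 = 0.697); two-sided 95% Wilson interval. With p = x/n and z = 1.96,

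lower bound = [p + z²/(2n) − z√(p(1−p)/n + z²/(4n²))] / (1 + z²/n).

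0.70 × 55 = 38.5, rounded up to x = 39. The bound is 57.9%, which matches the stated 58%. Rounding up also reproduces the other rows of Table 7: 36/55 gives 52.3%, 42/55 gives 63.7%, 44/55 gives 67.6% and 47/55 gives 73.8%. The sample-size figures are sound.

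**4. Size.** One participant is 1/55 = 1.8 points. The documents give no frequency, so k, the number of the 39 responders exchanged before any caplacizumab, is an assumption, shown here from 0 to 3.

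| k | Scored as non-responders | Lower bound | Removed from the analysis | Lower bound |
|---|---|---|---|---|
| 0 | 39/55 = 70.9% | 57.9% | 39/55 = 70.9% | 57.9% |
| 1 | 38/55 = 69.1% | 56.0% | 38/54 = 70.4% | 57.2% |
| 2 | 37/55 = 67.3% | 54.1% | 37/53 = 69.8% | 56.5% |
| 3 | 36/55 = 65.5% | 52.3% | 36/52 = 69.2% | 55.7% |

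**The case against.** The strongest reply is that the regimen is defined throughout as treatment without first-line TPE, so enrolling an exchanged patient would contradict the design. That is fair as a reading of intent. But the statement in Section 4.1 describes treatment on study and is not an entry criterion, and Section 5 bars waivers, so the written list governs.

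A second reply is that needing TPE means needing it on the study regimen. An exchange given before caplacizumab is not a failure of that regimen, and scoring it automatically as non-response could bias the rate downward. This stands. The documents do not settle the choice between rescoring and removal, and at k = 3 the two lower bounds differ by 3.4 points (55.7% against 52.3%). It is a reason to show both as sensitivity analyses and leave the primary responder rule alone.

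Third, loss from the mITT through a raised baseline ADAMTS13 works against inflation of the rate. That is also right, but it catches only some of the participants concerned.

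A reader might also infer that all TPE before enrolment goes uncounted. The SAP does not support that: it counts an exchange given after a marketed dose.

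**Conclusion.** The gap is real. Under both documents, a participant exchanged before any caplacizumab, not exchanged again and still below 10% ADAMTS13 at baseline can be a primary responder. What is at stake is the estimate and how it is read, at 1.8 points per participant.

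Two stronger readings are tempting and not supported:
- **That the primary result is inflated.** The documents give no count of such participants, and it may be zero.
- **That the trial could pass or fail on this.** Neither document sets a success criterion or a formal test. The 54% in the footnote to Protocol Table 7 is the upper confidence limit for overall remission in a comparator arm that received TPE; it is not a threshold for TPE-free remission. Even as an informal reference, the lower bound falls below it only when three or more of the 39 responders are rescored, and not when three are removed.

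The sizes assume 39 responders among 55, the planning case. The check covers the readable text only: Figure 1 and the redacted passages could not be read, so a relevant statement there cannot be ruled out.

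**What to change.** 1. Use one start point for the overall study period in Protocol 9.2.1 and SAP 3.1.
2. In SAP 5.4, identify every plasma exchange or plasma infusion record for the presenting episode, including those before the first caplacizumab dose, and list the participants concerned.
3. Pre-specify two sensitivity analyses of the primary endpoint: one scoring these participants as non-responders, one excluding them.
4. If enrolment continues, state in Section 5.2 whether TPE or plasma for the presenting episode before enrolment is allowed, in line with the design without first-line TPE.

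The cost is a SAP revision, a little more analysis work and one eligibility statement at the next amendment. The responder rate in the sensitivity analyses may come out slightly lower. If there are no such participants, an empty listing shows that the TPE-free claim is clean.
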